2.1.4 Safety endpoints

The safety analysis will be based on the reported adverse events (AEs), serious AEs (SAEs) and adverse events of special interest (AESIs). Other safety information, such as clinical laboratory data, and vital signs will also be assessed as applicable.

Observation period

There are 3 parts in the observation period:

- **Screening** period is defined as the time from the signed informed consent date up to the time prior to first dose of IMP.
- **On-treatment** period is defined as the day from the first dose of the IMP to the last dose of the IMP + 60 days.
- **Post-treatment** period is defined as the time after the last dose of IMP +60 days.

The treatment-emergent adverse event (TEAE) period is the **on-treatment** period.

The on-study observation period is defined as the time from start of treatment until the end of the study (defined as last protocol planned visit or the resolution/stabilization of all serious adverse events and AESI).

2.1.4.1 Adverse events variables

Adverse event observation period

- Pre-treatment AEs are AEs that developed or worsened or became serious from the signed informed consent date up to first administration of IMP
- TEAEs are AEs that developed or worsened or became serious during the TEAE period
- Post-treatment AEs are AEs that developed or worsened or became serious during the post-treatment period

All AEs (including SAEs and AESIs) will be coded to a “LLT”, “PT”, “HLT”, “HLGT”, and associated primary “SOC” using the version of MedDRA currently in effect at Sanofi at the time of database lock.

The occurrence of AEs (including SAEs and AESIs) will be recorded from the time of signed informed consent until the end of the study.

Adverse events of special interest (AESI; serious and nonserious) include the following:

- Grade ≥ 2 infusion related reactions (Infusion related reactions are defined as any signs or symptoms experienced by patients who receive IMP within 24 hours of the start of infusion)
- Grade ≥ 2 hypersensitivity reactions
- Grade 4 neutropenia ($ANC < 500/mm^3$)

- Grade 4 neutropenia with concurrent invasive infection (ANC<500/mm³)
- Increase in alanine transaminase (ALT) $\geq 3X$ ULN (for patients with normal baseline) or $>3X$ ULN AND at least 2-fold increase from baseline value (for patients with abnormal baseline)
- Invasive bacterial or fungal infections of clinical significance with confirmed diagnosis based on the Investigator's assessment with appropriate diagnostic workups and consultations
- Symptomatic overdose (serious or nonserious) with IMP
 - An overdose (accidental or intentional) with the IMP is an event suspected by the Investigator or spontaneously notified by the participant (not based on systematic pills count) and defined as an increase of at least 30% of the dose to be administered in the specified duration or if the dose is administered in less than half the recommended duration of administration.

AESIs will be flagged in the database using search criteria. All AEs captured on the general AE form, the ALT increase form, infusion reaction symptoms form, and the infection event form will be searched. The list of search criteria is provided in [Appendix C](#).

2.1.4.2 Deaths

The deaths observation periods are per the observation periods defined above.

- Death on-study: deaths occurring during the on-study period
- Death post-study: deaths occurring after the end of study

2.1.4.3 Laboratory safety variables

Clinical laboratory data will include hematology, clinical chemistry, urinalysis and infection tests. Clinical laboratory values will be converted to standard international units; international units will be used in all listings and tables.

Hematology and chemistry data will be collected at screening, baseline, days 2 or 3 (only for patients with second dose), 4, 7, 15, 21 and 29 or discharge. The laboratory parameters will be classified as follows:

- Hematology
 - **Red blood cells and platelets and coagulation:** hemoglobin, hematocrit, platelet count, red blood cell (RBC) count, and RBC indices (MCV, MCH, %Reticulocytes).
 - **White blood cells:** white blood cell (WBC) count and WBC differential (neutrophils, lymphocytes, monocytes, basophils, eosinophils)
- Clinical chemistry
 - **Metabolism:** total proteins, CRP, and glucose (fasting or non-fasting)

- **Electrolytes:** sodium, potassium, and calcium.
- **Renal function:** creatinine, and blood urea nitrogen (BUN).
- **Liver function:** alanine aminotransferase (ALT)/SGPT, aspartate aminotransferase (AST)/SGOT, alkaline phosphatase (ALP), total and direct bilirubin
- Ferritin
- D-dimer

Urine samples will be collected as follows:

- **Urinalysis** - dipstick: pH, blood, glucose, protein, ketones, nitrates, leukocyte esterase, and bilirubin.
- Specific gravity

Infection tests include:

- Bacterial and fungal blood culture

2.1.4.4 Vital signs variables

Vital signs variables include heart rate, respiratory rate, systolic blood pressure, diastolic blood pressure (daily until discharge). It also includes height and weight at screening only.

2.1.4.5 Physical Examination

A targeted physical examination including lung auscultation and assessment of consciousness will be performed at time points specified in protocol.

2.1.4.6 Electrocardiogram variables

A standard 12-lead ECG will be performed optionally at time points specified in protocol. Heart rate will be recorded from the ventricular rate and the PR, QRS, and QT (identify QTcB or QTcF) intervals will be recorded in the eCRF.

2.1.4.7 Anti-sarilumab antibodies

Samples analyzed in the antidrug antibody (ADA) assay will be categorized as either positive or negative.

ADA positive patient is defined as patient with at least 1 treatment-emergent or treatment-boosted ADA positive sample during the TEAE period, where

- Treatment-emergent ADA positive patient is defined as a patient with non-positive assay (meaning negative or missing) response at baseline but with a positive assay response during the TEAE period.
- Treatment-boosted ADA positive patient is defined as a patient with a positive ADA assay response at baseline and with at least a 4-fold increase in titer compared to baseline during the TEAE period.

ADA negative patient is defined as patient without a treatment-emergent or treatment-boosted ADA positive sample during the TEAE period.

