22. Sarilumab concentration
  - Day 1 sampling: 2 samples with one taken pre dose, and 1 taken within 30 min after the end of infusion; end of infusion sample should be collected from the arm contralateral to that used for IV infusion

- For patients administered a 2nd dose, Day 2 or Day 3 sampling is performed with 2 samples taken on the day of the 2nd dose, with 1 taken pre dose, and 1 taken within 30 min after the end of infusion; end of infusion sample should be collected from the arm contralateral to that used for IV infusion
- Day 4 (approximately 72 hours post first dose)
- The Day 29 or Early Discharge PK sample may be used for ADA analysis

23. In the event of any SAE of severe infusion reaction, or any AESI of anaphylactic reaction or systemic allergic reaction that is related to IMP, ADA samples will be collected at or near the onset of the event for any additional analysis.

24. Serum IL-6 samples must be taken pre-dose. Samples are mandatory for baseline/Day 1, Discharge before Day 29 and Day 29. It is optional on Day 4, 7, 15, and 21.

25. Serum sIL-6R:

- Day 1 sample taken pre dose (as close to initiation of treatment as reasonable)

26. Blood collected will be shipped for the central analysis of SARS-CoV-2 viral load and is not for determining the inclusion criteria.

27. Separate consent is required for participation in the optional genomic sub-study and collection of a blood sample for (DNA/RNA). The sample for genomic DNA/RNA should be collected on Day 1 or may be collected at any visit.

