2.4.5.7 Analyses of anti-sarilumab antibodies

The following summary will be provided separately for ADA positive patient, ADA negative patient.

ADA prevalence and titer

The following summary will be provided based on the ADA population:

- Number (%) of patients with an ADA positive sample at baseline
 - The summary statistics (including number, median, Q1, Q3, minimum and maximum) of the titer for the baseline ADA positive patients
- Number (%) of patients with an ADA negative sample at baseline

ADA incidence and titer

The following summary will be provided based on the ADA population during TEAE period:

- Number (%) of ADA-negative patients
- Number (%) of ADA-positive patients
 - The summary statistics (including number, median, Q1, Q3, minimum, and maximum) of the peak post-baseline titer for all ADA-positive patients
- Number (%) of treatment-emergent ADA-positive patients.

- The summary statistics (including number, median, Q1, Q3, minimum, and maximum) of the peak post-baseline titer for treatment-emergent ADA-positive patients
- Number (%) of treatment-boosted ADA positive patients.
- The summary statistics (including number, median, Q1, Q3, minimum, and maximum) of the peak post-baseline titer for all treatment-boosted ADA-positive patients

In addition, number (%) of patients with ADA positive or negative response at each visit will be summarized by treatment group.

Plot of percentage of patients with treatment-emergent ADA positive response at each visit will be provided by treatment group.

Listing for ADA status will also be provided.

ADA and PK

Descriptive summary of sarilumab concentrations in serum will be provided by ADA patient classifications (positive or negative) over time for the sarilumab treatment group by number of sarilumab doses.

ADA and clinical efficacy

The primary and key secondary efficacy endpoints will be analyzed by ADA patient classifications (positive or negative).

ADA and clinical safety

The safety assessment will focus on the following events:

- Hypersensitivity (standardized MedDRA query (SMQ): Hypersensitivity [Narrow])
- Anaphylaxis (SMQ: Anaphylaxis [Narrow])
- IV infusion reaction (HLT: IV infusion reaction)
- TEAEs leading to permanent treatment discontinuations

Number (%) of patients with these events will be summarized by ADA patient classifications (positive or negative) for the sarilumab treatment group.

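### The SAP's two-class ADA definition puts pre-existing, non-boosted antibodies in the negative row, so its table of reactions by ADA class is poorly suited to detecting acute reactions linked to them

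*SAP*

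**What the plan says.** **Classes.** Under SAP 2.1.4.7 an "ADA positive patient is defined as patient with at least 1 treatment-emergent or treatment-boosted ADA positive sample during the TEAE period". Treatment-emergent means "a patient with non-positive assay (meaning negative or missing) response at baseline but with a positive assay response during the TEAE period". Treatment-boosted means "a positive ADA assay response at baseline and with at least a 4-fold increase in titer compared to baseline during the TEAE period". Everyone else is negative: an "ADA negative patient is defined as patient without a treatment-emergent or treatment-boosted ADA positive sample during the TEAE period". There is no third class.

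**Use.** SAP 2.4.5.7 (ADA and clinical safety) lists hypersensitivity, anaphylaxis, IV infusion reaction and TEAEs leading to permanent discontinuation, and adds: "Number (%) of patients with these events will be summarized by ADA patient classifications (positive or negative) for the sarilumab treatment group".

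**Timing.** SAP 2.4.3.1 describes one dose on Day 1 and at most one more, 24 to 48 hours later. SAP 2.1.4.1 says: "Infusion related reactions are defined as any signs or symptoms experienced by patients who receive IMP within 24 hours of the start of infusion". The Protocol 1.3 schedule places ADA samples at baseline, Day 15, Day 29 and early discharge. Footnote 23 covers serious severe infusion reactions and IMP-related AESIs of anaphylactic or systemic allergic reaction; for these, "ADA samples will be collected at or near the onset of the event for any additional analysis".

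**Other ADA outputs.** SAP 2.4.5.7 also plans baseline prevalence with titers, ADA response by visit and an ADA listing. Protocol 9.4.5.3 lists results by patient and visit. No output crosses reactions with baseline ADA status.

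**The concern.** The emergent-or-boosted rule suits a count of how often treatment induces antibodies. Reused for acute reactions, it has two weaknesses.

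First, an antibody that could take part in a reaction to the first infusion has to be present by then, and the scheduled sample that shows this is the Day 1 pre-dose one. A patient positive in that sample, without a 4-fold rise later, goes into the comparison row.

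Second, for acute events the positive label is mostly assigned after the outcome. A reader of the two-row table could conclude that antibodies and infusion reactions are unrelated when the relevant antibodies were filed as negative. Protocol 2.3 names the IV route as an uncertainty of this study, and Grade 2 or higher infusion-related and hypersensitivity reactions are among its secondary safety objectives, so the table will be read with that question in mind.

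**Working it through.** The plan states no figure for this table, so there is none to reproduce. The check traces the definitions and then gives an illustration.

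**1. Pattern trace (SAP 2.1.4.7)**

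| Baseline | After dosing | Class |
|---|---|---|
| Positive | Rise below 4-fold | Negative |
| Positive | Rise of 4-fold or more | Positive |
| Negative | Positive | Positive |
| Missing | Positive | Positive, even if the antibody was already there |
| Negative or missing | Never positive | Negative |

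Carriers reach the positive row only by boosting, or through a missing baseline. The second route is possible because Protocol 1.3, footnote 2, speaks of baseline samples being collected only if obtained.

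**2. Time order.** The last possible dose is 48 hours after the first. Adding the 24-hour window gives 72 hours, about Day 4. The first fixed post-dose ADA sample is Day 15. A discharge sample could come earlier, so the order is general rather than absolute. The 24-hour window belongs to the AESI definition; the infusion-reaction item in 2.4.5.7 is a MedDRA term with no window of its own.

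**3. Illustration.** None of these inputs is in the documents: carriers q = 3% (range 1% to 5%); newly emergent antibodies t = 5%, all arising after the reaction window; reaction risk 20% in carriers and 2% in others; f = share of carriers who reach the positive row.

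With f = 0:
- Positive row: 2.0%.
- Negative row: (0.03 × 0.20 + 0.92 × 0.02) / 0.95 = 0.0244 / 0.95 = 2.57%.
- Ratio: 2.0 / 2.57 = 0.78. It is 0.91 at q = 1% and 0.68 at q = 5%.
- With q from 2% to 10% and t from 5% to 10%, the ratio runs from 0.84 to 0.50, and carriers supply 18% to 56% of the reactions in the negative row.

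With f = 0.30:
- Positive row: (0.05 × 0.02 + 0.009 × 0.20) / 0.059 = 0.0028 / 0.059 = 4.75%.
- Negative row: (0.92 × 0.02 + 0.021 × 0.20) / 0.941 = 0.0226 / 0.941 = 2.40%.
- Ratio: about 2.0.

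If 30% of carriers lack a baseline and are positive after dosing, and 30% of the rest are boosted, then f = 0.30 + 0.70 × 0.30 = 0.51. The positive row becomes (0.001 + 0.0153 × 0.20) / 0.0653 = 6.2%, the negative row (0.0184 + 0.0147 × 0.20) / 0.9347 = 2.3%, and the ratio about 2.7.

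The ratio crosses 1 where f = t / (1 − q) = 0.05 / 0.97 = 5.2%. Reversal therefore needs almost no carrier to reach the positive row; above that share the association is diluted instead. The by-baseline ratio of 10 is simply the input (20% / 2%).

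**4. Expected counts, one planned arm of about 160 (SAP 1.3), f = 0**
- Positive row: 160 × 0.05 = 8 patients; 8 × 0.02 = 0.16 reactions; chance of none 0.98^8 = 85%.
- Baseline-positive row: 160 × 0.03 = 4.8, about 5 patients; 5 × 0.20 = 1 reaction; chance of none 0.80^5 = 33%.

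**The case against.** Several counter-arguments have force.

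- **A reader might infer that the table cannot show antibody-driven reactions at all.** The documents do not support that. Boosted carriers, and carriers with a missing baseline who test positive later, enter the positive row. Hypersensitivity and anaphylaxis are counted through the TEAE period, to 60 days after the last dose, so for later-onset events the emergent-or-boosted class need not follow the outcome.
- **A reader might infer that baseline ADA results go unused beyond a prevalence count.** Also not so. Baseline status and titer define the classes, titers are summarized, and listings would let someone match a few reactions to baseline results by hand. What is missing is a planned summary that does it.
- **A reader might infer that footnote 23 builds in a false positive association.** The trigger is narrow, a baseline-positive patient still needs a 4-fold rise, and the SAP does not say how these samples are used. The extra chance of a positive finding among reactors is real but unquantified. These are also the only ADA samples timed to the event, so discarding them outright would lose information.
- **Scale and role.** ADA is not among the listed objectives or endpoints, the table is an untested n (%), and no decision rule depends on it. Expected counts are tiny under either classification.

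These points limit the strength and consequence of the finding. They do not change the classification of non-boosted carriers or the general timing of the scheduled samples.

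**Conclusion.** The concern holds in a limited form. By definition, pre-existing non-boosted antibodies are filed as ADA negative, and positivity always rests on a post-dose sample that, outside footnote 23, generally follows the infusion-reaction window. The planned table is therefore poorly suited to detecting acute reactions linked to pre-existing antibodies, and it can dilute or reverse such an association.

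The size is unknown. The ratios above show direction under assumed inputs and must not be read as estimates: 0.84 to 0.50 if no carrier reaches the positive row, and about 2 to 2.7 against a true 10 at the 3% and 5% inputs if 30% to 51% do. That carriers face a higher reaction risk is itself an assumption. Efficacy conclusions are unaffected. The change is worth making because the pre-dose sample is already scheduled.

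**What to change.** 1. In SAP 2.1.4.7 and the 2.4.5.7 safety table, show three classes: pre-existing non-boosted, treatment-emergent or boosted, and never positive.
2. Add a descriptive table of infusion reactions, and of hypersensitivity or anaphylaxis with onset within 24 hours of an infusion, by pre-dose ADA status (positive, negative, missing).
3. Keep the treatment-emergent or boosted class for later-onset events.
4. Show the classification with and without the footnote 23 samples, and state in the SAP how they are used.

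Cost: SAP wording, one extra class and one added table, with no new sampling. Because 2.4.5.7 also uses the classes for PK and efficacy, the SAP should say whether those summaries keep two classes. The downside is that the baseline-positive row will hold few patients (about 5 per planned arm at an assumed 3%), so the result is descriptive only and a zero in that row would not be reassuring.

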2.1.5 Pharmacokinetics variables

Sarilumab concentration will be collected at Day 1, 2 or 3 (only for patients with second dose), Day 4, 7, 15, 21 and 29 or early discharge.

2.1.6 Biomarker and other variables

Measurement of SARS-CoV-2 (Blood sample) or SARS-CoV-2 (NP swab), and the concentration of CRP, IL-6 and sIL-6R will be collected by schedule specified in protocol.

2.2 DISPOSITION OF PATIENTS

This section describes patient disposition for both patient study status and the patient analysis populations.

Screened patients are defined as any patients who met the inclusion criteria and signed the informed consent.

Randomized patients consist of all patients with a signed informed consent form and randomized, regardless of whether the study drug was used.

The total number of patients for each one of the following categories will be presented in the clinical study report (CSR) using a summary table:

- Screened patients
- Screen failure patients and reasons for screen failure
- Randomized patients
- Randomized but not treated patients
- Randomized and treated participants
- Patients who reached Day 29 (while still hospitalized)
- Patients who did not reach Day 29 and the reasons

- Patients who completed the follow-up (Day 60)
- Patients who did not complete follow-up (Day 60) and main reason for not completing follow-up.

In addition, the number (%) of patients screened, randomized, reached Day 29 and completed follow-up to Day 60 will be provided by country and site.

All critical or major deviations potentially impacting efficacy analyses, randomization and drug dispensing irregularities and other major/critical deviations will be summarized in tables giving numbers and percentages of deviations by treatment group.

Additionally, the analysis populations for safety, efficacy, per protocol, and PK/PD/Immunogenicity will be summarized in a table by patient counts based on the randomized populations (see definitions in [Section 2.3](#)).

- ITT population (Randomized population)
- Efficacy population (modified intention-to-treat (mITT))
- Per protocol population (PPS)
- Safety population
- PK population
- ADA population

2.2.1 Randomization and drug dispensing irregularities

Randomization will be monitored throughout the study and reviewed on an ongoing basis. Any drug-dispensed wrongly will be identified and documented by manual deviation.

All randomization and drug-dispensing irregularities will be documented in the clinical study report. If the number of irregularities is large enough to make a tabular summary useful, the irregularities will be categorized and summarized among randomized patients (number and percentages). Nonrandomized, treated patients will be described separately.

Randomization and drug-dispensing irregularities to be prospectively identified include but are not limited to:

Table 2 - Randomization and Drug Allocation Irregularities

Randomization and Drug Allocation Irregularities
Erroneous treatment dispensation (will be identified by manual deviation)
Kit not available
Randomization by error
Subject randomized twice
Forced randomization

2.3 ANALYSIS POPULATIONS

Enrolled population are all patients who sign the informed consent form (ICF).

Randomized population are all randomized patients regardless of IMP was administered.

The safety experience of patients treated and not randomized will be reported separately, and these patients will not be in the safety population.

2.3.1 Efficacy populations

2.3.1.1 *Intent-to-treat/Modified intent-to-treat population*

The intent-to-treat population (ITT) is the randomized population analyzed according to the treatment group allocated by randomization.

The modified intention-to-treat (mITT) population includes all randomized patients who received at least one dose of the study drug. Analysis of the mITT population will be done according to the initial treatment assigned to the patient (as randomized). The mITT population will be the primary population for analysis of primary and secondary efficacy endpoints, as well as for data including (but not limited to) demographics and baseline characteristics.

2.3.1.2 *Per-protocol population*

The Per Protocol population set (PPS) includes all ITT patients who did not have any relevant major protocol deviations, eg, patients who are randomized and treated, but do not have laboratory-confirmed SARS-CoV-2 infection will be excluded from PPS. The final determination of the exclusion of patients from the PPS will be made prior to the primary database lock. Analysis of the PPS will be done according to the treatment the patient received. The PPS will be used as sensitivity analysis for the primary efficacy endpoint.

